## 8.0 DATA QUALITY CONTROL AND DATABASE MANAGEMENT

- a) Data will be stored in a de-identified manner, with a CGP-coding scheme. The Safe Harbor method will be used to de-identify one PHI specific identifier (patient name) by creating a unique code for each patient. The list of patient names and codes will be kept in a separate and secure location, on an Idrive on Montefiore Computer system, with restricted access only to approved individuals. The data will be carefully entered and analyzed in statistical programs such as excel. The data will be checked and edited by the members of the research team. No individuals other than members of the research team will have access to the data. All lab personnel that work with patient data or samples have passed human subject protection courses, and certification of this is on file in the IRB office. All physical data are kept in a designated site, in a locked cabinet in a lockable room.
- b) Subject treatment assignments will remain blinded until the final subject has completed follow up and all data has been recorded and validated. Urgent, immediate unblinding due to medical emergency may be authorized by the Investigator. All instances of subject unblinding will be documented in the study record.

## 10.0 APPENDICES

### Appendix A: HS-PGA Score

Disease severity, measured by HS-PGA, is defined as follows:

- 0, clear
- 1, minimal: noninflammatory nodules
- 2, mild: fewer than 5 inflammatory nodules or 1 abscess/draining fistula with no inflammatory nodules
- 3, moderate: 5 or more inflammatory nodules, or 1 abscess/draining fistula and at least 1 inflammatory nodule, or 2 to 5 abscesses/draining fistulas and fewer than 10 inflammatory nodules
- 4, severe: 2 to 5 abscesses/draining fistulas and at least 10 inflammatory nodules
- 5, very severe: more than 5 abscesses/draining fistulas

### Appendix B: NRS Pain Scale

The patient-reported NRS for pain is an 11-point NRS ranging from 0 (no pain) to 10 (worst possible pain).

### Appendix C: Hurley Staging

- Stage 1: Single or multiple abscesses without sinus tract formation or scarring
- Stage 2: Recurrent abscesses with one or more sinus tracts and scarring widely separated by normal skin
- Stage 3: Diffuse involvement with multiple sinus tracts and no intervening normal skin

## Appendix D: Patient Satisfaction Survey

1. What is your race?
  - a. Caucasian
  - b. Black/African American
  - c. American Indian/Alaska Native
  - d. Asian Indian
  - e. Chinese
  - f. Filipino
  - g. Japanese
  - h. Korean
  - i. Vietnamese
  - j. Other Asian
  - k. Native Hawaiian
  - l. Guamanian/Chamorro
  - m. Samoan
  - n. Other Pacific Islander
  - o. Other \_\_\_\_\_ (Please specify)
2. What is your ethnicity?
  - a. Hispanic/Latinx/Spanish origin
  - b. Not Hispanic/Latinx/Spanish origin
3. Please rate your current flare or lesions.
  - a. Clear
  - b. Minimal
  - c. Mild
  - d. Moderate
  - e. Severe
  - f. Very severe
4. On a scale from 0 to 10, with 0 being an example of someone with no pain and 10 being the worst pain possible, where would you rate your pain at rest?

5. On a scale from 0 to 10, with 0 being an example of someone with no pain and 10 being the worst pain possible, where would you rate your pain when HS lesions present today are touched?

6. How would you rate the drainage of your current flare?

- a. None
- b. A little
- c. Some
- d. A lot
- e. The most I've ever had

7. Using the following scale:

(5) Excellent (4) Very good (3) Good (2) Fair (1) Poor

how would you rate your current.....

- a. Disease control?
- b. Mobility?
- c. Ability to sleep for the past two nights?
- d. Mood?
- e. Quality of life?

8. How satisfied are you with the steroid injections?

- 1. Very satisfied
- 2. Satisfied
- 3. Neutral
- 4. Dissatisfied
- 5. Very dissatisfied

9. If response to number 8 was dissatisfied or very dissatisfied, please explain why.

10. Would you be willing to undergo steroid injections again?

1. Yes
2. No

10a. If response to number 10 was no, please explain why.

## Appendix E: Ordinal Scale to Grade Erythema and Edema

Visual assessment ordinal scale to grade skin erythema

- 0, no erythema
- 1, very faint erythema: skin has a very light pink color
- 2, faint erythema, skin reaction is more apparent with clear borders but is still pink with more intensity
- 3, bright erythema, erythema is apparent in bright pink and borders are clearly defined
- 4, skin is bright red, borders are very well defined, capillaries and bruising may be visible

Assessment ordinal scale to grade edema

- 0, no edema (soft)
- 1, moderate to severe edema (soft to hard)
- 2, fluctuant

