## 1.0 BACKGROUND/SIGNIFICANCE

Hidradenitis suppurativa (HS) is a chronic recurrent inflammatory disease of hair follicles primarily localized to the axillae, inframammary folds, suprapubic and inguinal skin, upper inner thighs, perineum, and buttocks. Early manifestations of HS include tender nodules that may progress into fluctuant abscesses. As the disease advances, recurrent inflammatory nodules and abscesses may develop permanent connecting dermal tracts (“tunnels”). Although the pathogenesis is poorly understood, HS is considered a disorder of follicular occlusion. The most recent estimate of HS prevalence in the United States is 0.10%; however, African Americans, females, and young adults are disproportionately affected. The median age of onset in females is 19 years and in males is 23 years. However, cases are reported in pediatric patients as early as 13 years old. Furthermore, HS is associated with a wide range of comorbidities, including cardiovascular, endocrine, gastrointestinal disorders, and psychiatric comorbidities, such as depression, anxiety, bipolar illness, and schizophrenia. There is not only greater disability and decreased quality of life compared to all other dermatologic conditions, but also the complexity and profound debilitation make management difficult and costly.

For more than 50 years, a standard therapy for acute HS flares has been the subcutaneous injection of triamcinolone, a fluorinated corticosteroid, into inflammatory nodules, abscesses and sinus tracts. The proposed mechanism involves activation of the glucocorticoid receptor, which blocks synthesis of leukotrienes and reduces the production of proinflammatory cytokines, including interleukin-1. Additionally, this therapy may inhibit cytotoxic T-cell activation.

Previous studies documented the efficacy of intralesional triamcinolone in decreasing erythema, edema, suppuration, and size of lesion, as well as patient-reported pain. Despite the proposed benefits of therapy, no standard effective dose has been established. Riis et al. conducted a prospective case series utilizing 10 mg/mL with the volume of injection based on patient lesion size, while Alvarez et al. performed a prospective open-label study injecting 40 mg/mL with a volume of 0.2-1 mL per fistulous tract.

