#### c) Outcome Measures Pertaining to Each Aim

- *Aim 1:* To compare efficacy of ILTAC-10, ILTAC-20, and ILTAC-40 versus placebo, we will measure the change from baseline in pain, objective and subjective markers of inflammation, physical functioning, and lesion size as well as comparing these changes among the different treatment groups. Change from pain baseline will be quantified by comparison of the NRS pain scale across different treatment groups (Appendix B). Objective markers of inflammation include c-reactive protein (CRP), erythrocyte sedimentation rate (ESR), and interleukin-6 (IL-6), which will be obtained from chart review of standard of care initial, 2 week, and 4 week follow-up HS visit. Erythema and edema will be measured clinically based on a 5-point ordinal scale (Appendix E). Suppuration will be measured on a dichotomous scale, by the presence or absence of purulent drainage from the lesion. Physical functioning will be measured by change from baseline in the Patient-Reported Outcomes Measurement Information System (PROMIS) measure of physical functioning. Separate forms will be administered for adult and pediatric participants. A one point change, either positive (improvement) or negative (decline), will be considered clinically meaningful (Appendix F and Appendix G). Lesion size will be measured in centimeters at baseline and during the week 2 and 4 visit.

- *Aim 2:* Side effects of ILTAC-10, ILTAC-20, and ILTAC-40 that will be investigated include thinning/atrophy of the skin, acneiform lesions, capillary dilations, and dyschromia. Hypothalamic-pituitary-adrenal (HPA) axis suppression will be obtained through chart review of standard of care serum 8 AM cortisol and ACTH levels at week 2 and 4 follow-up HS visits. Self-evaluations will be conducted by the patient and documented via telephone interviews. Clinical-evaluations will be conducted at the follow-up visits.
- *Aim 3:* To measure the patient's satisfaction after treatment, we will compare the results from the satisfaction survey between the different treatment groups at baseline, day 2, day 6, week 2, and week 4. The patient satisfaction survey will address disease control, and response to injection (in terms of pain, drainage, and lesion size), and quality of life (Appendix D).

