## 7.0 DATA ANALYSIS

- a) Statistical Methods  
We will analyze the data from the study using an intention to treat approach. Categorical variables, including presence of side effects, drainage, and physical function, will be analyzed with chi square tests. Continuous variables, such as NRS pain scale, markers of inflammation, and lesion size, will be analyzed by T-test. Sensitivity analyses or exploratory analyses may be performed to examine the effect difference for race or gender. In the unlikely case patients do not receive the treatment they will still be randomized for analysis using a per protocol approach. All statistical tests will be 2-sided, with  $p < 0.05$  considered significant.
- b) There will be no interim analysis or early stopping of the study.
- c) Confounding and effect modification will be addressed by randomization of the subjects and blinding of both the investigators and the participants.
- d) If subjects are lost to follow up, they will be analyzed in the group to which they were initially randomized.

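### The erythema scale is anchored to pink and red with no provision for darker skin, which may blunt this secondary outcome and make any race comparison of it unreadable

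*Combined protocol and SAP*

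**What the plan says.** Section 2.0c (Aim 1) names the instrument: "Erythema and edema will be measured clinically based on a 5-point ordinal scale (Appendix E"). No device-based measure of erythema is mentioned. Change in erythema at weeks 2 and 4 is part of one secondary outcome (Section 2.0a, Secondary Outcomes).

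After grade 0 (none), Appendix E gives four erythema grades. The lowest of them is defined by colour alone: "1, very faint erythema: skin has a very light pink color". The two middle grades stay in the pink range, a stronger pink for grade 2 and a vivid pink for grade 3, and both add that the edges of the lesion can be made out. The top grade moves from pink to red: "4, skin is bright red, borders are very well defined, capillaries and bruising may be visible". No grade refers to the patient's own surrounding skin.

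On the population, Section 1.0 states that "African Americans, females, and young adults are disproportionately affected". On analysis, Section 7.0a lists markers of inflammation among the variables compared by t-test and adds that "exploratory analyses may be performed to examine the effect difference for race or gender".

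The assessor is blinded and trained, and the training covers subjective markers of inflammation but does not mention skin tone (Section 2.0a, Randomization and Blinding). Race and ethnicity are taken from the chart and photographs are obtained (Section 2.0b, Visit 1). Skin tone is not recorded.

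**The concern.** The scale asks the assessor to match a lesion to a named shade. If inflamed skin in a darker-skinned patient does not look pink or red, no grade above 0 fits well. An assessor who follows the wording would tend towards 0 or a low grade, and one who improvises is no longer using the stated scale.

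Eligibility requires an inflamed nodule or abscess but no minimum erythema grade. Patients who score low at baseline can therefore enter, with little room to improve.

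Two things are at stake. The first is the sensitivity of the erythema outcome to a real ILTAC effect. The second is the meaning of any comparison of that effect by race. Because skin tone is not recorded, the problem could not be diagnosed directly afterwards. The protocol criticises the earlier saline-controlled trial for not addressing markers of inflammation, so measuring them soundly is part of this trial's own rationale.

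**Working it through.** **1. What rests on colour.** Grade 1 has a colour and nothing else. Grades 2, 3 and 4 each have a colour plus a statement about borders, and grade 4 also mentions capillaries and bruising. So all four non-zero grades carry a pink or red anchor, three of the four have a second cue, and the lowest step off zero has none.

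**2. The plan's only power figure.** Section 3.0b concerns NRS pain, not erythema. With SD 1 at both times and correlation 0.1, the SD of change is √(1 + 1 − 2 × 0.1) = √1.8 = 1.342. With 30 per arm, a difference of 1 and two-sided alpha 0.05, the noncentral t gives 0.8102 against the stated 0.81021. It reproduces, and nothing here changes it.

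**3. How under-scoring acts on a change score.** Let b and f be the true grades at baseline and follow-up, and suppose a patient is under-scored by k grades. The observed change is max(0, f − k) − max(0, b − k).

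- If b and f are both at least k, this equals f − b. The shift cancels.
- If b is at least k but f is below k, it equals −(b − k) whatever f is. Any further improvement is invisible. With k = 2, true follow-up grades of 0, 1 and 2 all read as 0.
- If both are below k, the observed change is 0.

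The harm therefore comes from the floor, and it removes true differences rather than inventing them.

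**4. Illustration, all erythema inputs assumed.** True baseline grade has mean 2.5 and SD 0.9, saline change is −0.5, the added ILTAC effect is −1 grade, and residual SD is 0.9. Scores are rounded and cut to 0–4. There are 30 per arm and 20,000 simulated trials per row. Under-scored patients are equally likely in both arms.

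| Share under-scored | By (grades) | Observed difference | Power |
|---|---|---|---|
| 0% | – | −0.855 | 94.8% |
| 25% | 1 | −0.805 | 92.7% |
| 25% | 2 | −0.727 | 87.3% |
| 50% | 1 | −0.750 | 90.0% |
| 50% | 2 | −0.601 | 76.0% |
| 75% | 1 | −0.699 | 87.3% |
| 75% | 2 | −0.473 | 63.0% |

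The first row falls short of −1 because rounding and the limits of the scale already cost something without any under-scoring.

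With no true effect, the observed difference stayed at about 0 and the rejection rate with under-scoring was 4.8% to 5.1%. No false treatment effect appears.

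**5. By subgroup, same true effect of −1 in everyone.** The observed effect was about −0.86 in correctly scored patients. It was about −0.65 in those under-scored by 1 grade, a loss of 1 − 0.65/0.86 = 24%. It was about −0.35 in those under-scored by 2 grades, a loss of 1 − 0.35/0.86 = 59%. The apparent gap between subgroups, 0.21 to 0.51 grade, is produced entirely by the scale.

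**The case against.** The strongest reply is that the central premise is an inference. The documents report no under-scoring with this scale, and Section 1.0 describes disease burden in the United States, not the racial mix of this clinic. That stands, and it is why the point is worded as a possibility. A reader might infer that erythema will be under-scored in this trial; the documents do not show it.

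A reader might also infer that the treatment comparison is biased towards ILTAC or saline. It is not. Allocation is random, the assessor is blinded and the outcome is change from baseline, so under-scoring that is equal across arms can only pull the difference towards zero. Nor is a low-scoring patient necessarily unable to improve: a baseline grade of 1 can still fall to 0.

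The race analysis is optional and exploratory, with no outcome named, so a race comparison of erythema is possible rather than planned. Race is also only a proxy for skin tone. Both points limit the weight of this part, but the analysis would be hard to interpret if it were done.

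The grade 4 wording invites a further reading, that a side effect could distort the efficacy score, since capillary dilation is a listed ILTAC side effect (Sections 2.0c and 6.0, Appendix H). The support is thin. The text says capillaries and bruising may be visible, not that they define the grade. Saline patients are injected too, and the protocol's own hypothesis expects no difference in side effects between ILTAC and saline.

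Finally, the reach is small. Erythema is one of three components of one secondary outcome, and Aim 1 also uses pain, lesion size, edema, suppuration and blood markers. Training and photographs are partial safeguards, but neither is stated to address skin tone.

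**Conclusion.** The point holds as a measurement weakness in one secondary outcome. Every non-zero erythema grade is tied to pink or red, the plan offers no guidance for darker skin and no record of skin tone, and it names African Americans as disproportionately affected. The likely harm, if under-scoring occurs, is attenuation of the ILTAC-saline difference and a race comparison of erythema that cannot be interpreted. It is not a false treatment effect.

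The size cannot be estimated from the documents. The simulated range depends wholly on the assumed share under-scored (25% to 75%), the assumed shortfall (1 or 2 grades) and the assumed grade distribution, so it shows direction and mechanism only. NRS pain and the 30 per arm are untouched. The change is worth making because it is cheap, not because the trial's main conclusion depends on it.

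**What to change.** Before enrolment:

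- Reword erythema grades 1 to 4 in Appendix E relative to the patient's adjacent uninvolved skin, with descriptors for both lighter and darker skin.
- Include examples across skin tones in the assessor training already planned.
- Record skin tone at baseline, so that any race comparison of erythema can be read against it.
- As a minor tidy-up, drop capillaries and bruising from grade 4, so that a listed side effect does not sit inside an efficacy grade.

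The cost is one appendix revision, some added training material and one baseline field. The downside is that scores become less comparable with other uses of the original colour scale. No change to the sample size or the primary analysis follows.

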## Appendix F: PROMIS – Adult Physical Functioning

PROMIS® Item Bank v2.0 – Physical Function – Short Form 10a

### Physical Function – Short Form 10a

Please respond to each question or statement by marking one box per row.

|         |   | Not at all                    | Very little                   | Somewhat                      | Quite a lot                   | Cannot do                     |
|---------|---|-------------------------------|-------------------------------|-------------------------------|-------------------------------|-------------------------------|
| PFA1    | Does your health now limit you in doing vigorous activities, such as running, lifting heavy objects, participating in strenuous sports? ..... | 
5 | 
4 | 
3 | 
2 | 
1 |
| PFC36r1 | Does your health now limit you in walking more than a mile (1.6 km)?  | 
5 | 
4 | 
3 | 
2 | 
1 |
| PFC37   | Does your health now limit you in climbing one flight of stairs? .....  | 
5 | 
4 | 
3 | 
2 | 
1 |
| PFA5    | Does your health now limit you in lifting or carrying groceries? .....  | 
5 | 
4 | 
3 | 
2 | 
1 |
| PFA3    | Does your health now limit you in bending, kneeling, or stooping? .....   | 
5 | 
4 | 
3 | 
2 | 
1 |
|         |   | Without any difficulty        | With a little difficulty      | With some difficulty          | With much difficulty          | Cannot do                     |
| PFA11   | Are you able to do chores such as vacuuming or yard work? .....   | 
5 | 
4 | 
3 | 
2 | 
1 |
| PFA16r1 | Are you able to dress yourself, including tying shoelaces and buttoning your clothes? .....   | 
5 | 
4 | 
3 | 
2 | 
1 |
| PFB26   | Are you able to shampoo your hair? .....  | 
5 | 
4 | 
3 | 
2 | 
1 |
| PFA55   | Are you able to wash and dry your body?..   | 
5 | 
4 | 
3 | 
2 | 
1 |
| PFC45r1 | Are you able to sit on and get up from the toilet? .....  | 
5 | 
4 | 
3 | 
2 | 
1 |

## Appendix G: PROMIS – Pediatric Physical Functioning

PROMIS Pediatric Item Bank v2.0 – Mobility– Short Form 8a

### Pediatric Mobility – Short Form 8a

**Please respond to each question or statement by marking one box per row.**

| In the past 7 days... |  | With no trouble               | With a little trouble         | With some trouble             | With a lot of trouble         | Not able to do                |
|-----------------------|--|-------------------------------|-------------------------------|-------------------------------|-------------------------------|-------------------------------|
| 235R1r                | I could do sports and exercise that other kids my age could do ..... | 
5 | 
4 | 
3 | 
2 | 
1 |
| 4124R1r               | I could get up from the floor.....                                   | 
5 | 
4 | 
3 | 
2 | 
1 |
| 236R1r                | I could keep up when I played with other kids .....                  | 
5 | 
4 | 
3 | 
2 | 
1 |
| 3892R1r               | I could move my legs .....   | 
5 | 
4 | 
3 | 
2 | 
1 |
| 2646R1r               | I could stand up by myself.....                                      | 
5 | 
4 | 
3 | 
2 | 
1 |
| 4185R1r               | I could stand up on my tiptoes.....                                  | 
5 | 
4 | 
3 | 
2 | 
1 |
| 2707R2r               | I could walk up stairs without holding on to anything .....          | 
5 | 
4 | 
3 | 
2 | 
1 |
| 5023R1r               | I have been physically able to do the activities I enjoy most.....   | 
5 | 
4 | 
3 | 
2 | 
1 |

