##### *Secondary Outcomes*

- Change from baseline in NRS pain scale at days 2, 6, and 14.
- Difference in change from baseline in NRS pain scale at days 2, 6, 14, and 28 between ILTAC-10, ILTAC-20, ILTAC-40.
- Change from baseline in HS-PGA score at week 2 and 4.
- Difference in change from baseline in HS-PGA score at week 2 and 4 between ILTAC-10, ILTAC-20, ILTAC-40.
- Change from baseline in objective markers of inflammation (c-reactive protein [CRP], erythrocyte sedimentation rate [ESR], and interleukin-6 [IL-6]) at week 2 and 4.

- Change from baseline in subjective markers of inflammation (erythema, edema, and suppuration) at week 2 and 4.
- Change from baseline in lesion size at week 2 and 4.
- Difference in change from baseline in lesion size at week 2 and 4 between ILTAC-10, ILTAC-20, ILTAC-40.
- Change from baseline in Patient-Reported Outcomes Measurement Information System (PROMIS) measure of physical functioning at days 2, 6, 14, and 28.
- Difference in change from baseline in PROMIS at days 2, 6, 14, and 28 between ILTAC-10, ILTAC-20, ILTAC-40.
- Proportion of subjects reporting side effects at days 2, 6, 14, and 28.
- Difference in proportion of subjects reporting side effects at days 2, 6, 14, and 28 between ILTAC-10, ILTAC-20, ILTAC-40.
- Baseline patient satisfaction.
- Change from baseline in patient satisfaction at days 2, 6, 14, and 28.
- Serum cortisol and ACTH levels at week 2 and 4.
- Change in serum cortisol and ACTH levels from week 2 to 4.

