Participant eligibility will be assessed according to inclusion and exclusion criteria in 2.0a. A member of the study team will describe the study and answer any of the participant's questions. The participant will then be consented and enrolled. The initial visit and all subsequent visits will include documentation of NRS pain scale (Appendix B), HS-PGA, Hurley Stage (Appendix C), clinical markers of inflammation, and lesion size (as specified in our standard approach to care. Photographs of the lesions will be obtained. The study personnel will administer a patient satisfaction survey and the PROMIS questionnaire, which will take 15 minutes to complete (Appendix D and Appendix F [or Appendix G if pediatric]). Chart review will record demographic information (age, gender, race, ethnicity, smoking status, and BMI) and complete blood count (CBC), basic metabolic profile (BMP), liver function tests (LFT), erythrocyte sedimentation rate (ESR), c-reactive protein (CRP), and interleukin-6 (IL-6). The lab work is a standard of care at the HSC independent of research objectives. The patient will receive an injection, not to exceed 2 mL per anatomic area, in up to 3 anatomic areas (total of 3mL). The patient will be counseled regarding potential side-effects of the treatment (Appendix H) and asked to monitor accordingly. No other changes to the patient's HS medication regimen will be made for the duration of the study.

- Phone Contact 1 (2-day post-treatment)

Since triamcinolone has a half-life of 18 to 36 hours, the initial patient follow-up will be a phone call at 2 days post-injection, lasting 15 minutes. Study personnel will administer a patient satisfaction survey and the PROMIS questionnaire (Appendix D, and Appendix F [or Appendix G if pediatric]). Additionally, patients will be asked if they experienced any side effects, including thinning/atrophy of skin, acneiform lesions, capillary dilation, and/or dyschromia.

- Phone Contact 2 (6 days post-injection)

This 15 minute phone call will be 6 days post-injection and will involve administering the patient satisfaction survey, the PROMIS questionnaire, and questions about side effects.

- Visit 2 (2 weeks post-injection)

- The initial screening visit examination will be repeated at week 2. Additionally, the patient will be asked to identify side effects. A patient

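### The pediatric PROMIS form recalls 7 days but is given at days 2 and 6, so early change scores in minors partly describe the time before injection

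*Combined protocol and SAP*

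**What the plan says.** Section 2.0 a), Secondary Outcomes, lists change from baseline in the PROMIS "measure of physical functioning at days 2, 6, 14, and 28", and separately "Difference in change from baseline in PROMIS at days 2, 6, 14, and 28 between ILTAC-10, ILTAC-20, ILTAC-40".

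Section 2.0 b) sets the early contacts. For the first, "the initial patient follow-up will be a phone call at 2 days post-injection", at which staff administer "the PROMIS questionnaire (Appendix D, and Appendix F [or Appendix G if pediatric"]. For the second, "This 15 minute phone call will be 6 days post-injection and will involve administering the patient satisfaction survey, the PROMIS questionnaire" and side-effect questions. The Study Calendar in Section 5.0 f) marks PROMIS at enrollment, day 2, day 6, week 2 and week 4.

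Section 2.0 c), Aim 1, adds: "Separate forms will be administered for adult and pediatric participants". The pediatric instrument is "PROMIS Pediatric Item Bank v2.0 – Mobility– Short Form 8a" (Appendix G), and its item column is headed "In the past 7 days". The adult instrument, Physical Function Short Form 10a (Appendix F), asks whether health limits the patient now and what the patient is able to do. It prints no recall period.

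The plan does not shorten the pediatric recall period for the early calls or tell minors to answer only for the days since injection. It gives no separate analysis by form.

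**The concern.** The early calls are there to catch an early response. Section 2.0 b) justifies the day-2 call by the half-life of triamcinolone, and Section 1.0 expects relief within 12 to 24 hours. A form that looks back 7 days cannot isolate a response that is 2 days old, because most of what it asks about happened before treatment. The day-2 score also shares most of its window with the baseline score from which it is subtracted.

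Two things are at stake. A real early gain in function among minors would be understated at day 2 and slightly at day 6. And a single PROMIS outcome at those days would describe the present in adults and the past week in minors. In minors, the sliding window could also make an immediate benefit look like gradual improvement between day 2 and week 2.

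**Working it through.** The plan states no figure on this point, so there is none to reproduce. The check is a count of days, followed by an illustration of size.

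**Inputs from the documents**
- Recall period of the pediatric form: 7 days (Appendix G).
- PROMIS assessments: enrollment (the day of injection), then days 2, 6, 14 and 28 (Sections 2.0 a), 2.0 b) and 5.0 f)).
- Recall period of the adult form: none; it asks about current status (Appendix F).
- Minors can enroll: age above 13 (Section 2.0 a)), with assent for ages 13 to 17 (Section 5.0 d)).

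**Step 1: window count.** For an assessment *d* days after injection, recalled days before injection = max(0, 7 − *d*).

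| Day | Before injection | After injection |
|---|---|---|
| 2 | 5 of 7 (71%) | 2 of 7 (29%) |
| 6 | 1 of 7 (14%) | 6 of 7 (86%) |
| 14 | 0 of 7 | 7 of 7 |
| 28 | 0 of 7 | 7 of 7 |

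The baseline window is the 7 days up to injection. The pre-injection days in a later window therefore also lie in the baseline window: about 5 days of overlap at day 2 and 1 at day 6. This step needs no assumption beyond patients answering the form as printed.

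**Step 2: illustrative dilution in minors.** Assume the answer weights the 7 days equally and the effect is immediate and constant. The share of the true mean change that is observed is min(*d*, 7)/7.
- Day 2: 2/7 = 29%. Day 6: 6/7 = 86%.
- With onset after 1 day instead: (2 − 1)/7 = 14% and (6 − 1)/7 = 71%.
- If patients weight recent days more heavily, the shares are higher than under equal weighting.

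**Step 3: illustrative effect if the forms are pooled.** Let *q* be the share of minors, which the documents do not give; assume 5% to 30%. With equal true effects in adults and minors and immediate onset, the loss in the pooled mean effect = *q* × (pre-injection share).
- Day 2: 0.05 × 5/7 = 3.6%; 0.30 × 5/7 = 21.4%.
- Day 6: 0.05 × 1/7 = 0.7%; 0.30 × 1/7 = 4.3%.

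**The case against.** The strongest reply is that little depends on this. Only minors are affected, on a secondary outcome, at two time points, and day 6 has only one pre-injection day in its window. The primary outcome is NRS pain at week 4. Early response in minors is also covered by the NRS at days 2 and 6 (Section 5.0 f)) and by the satisfaction survey, which asks about present mobility and pain (Appendix D). All of that stands and limits the importance of the point. It does not make the day-2 pediatric change score interpretable as a post-treatment change.

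A second reply concerns scale. Section 7.0 a) puts physical function among the categorical variables for chi-square tests, and Section 2.0 c) treats a one-point change as meaningful. The percentages in the working describe a mean and do not carry over to a proportion. That is correct, and it is one reason to treat them as illustration only.

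A third reply is that recall is not the only difference between the forms. One has ten physical-function items and the other eight mobility items, so they differ at every visit. This also stands. It supports reporting by form throughout, not just at the early calls.

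A reader might also infer more than the documents support:
- That adult and pediatric scores will be pooled. The plan lists one PROMIS outcome and says separate forms are used, but never says how they are combined. The pooled figures are therefore conditional.
- That 29% is the most that minors could show at day 2. It follows only from equal weighting and is not a bound.
- That one arm is favored. The recall window is the same in every arm, so the expected effect is to shrink differences.

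**Conclusion.** The point holds as a minor design flaw. If the plan is followed as written, 5 of 7 recalled days at day 2 and 1 of 7 at day 6 precede treatment in minors, while adults report current status. The early PROMIS outcomes therefore measure different periods in the two age groups, and an early benefit in minors is pulled toward no difference. The problem is large at day 2 and small at day 6. PROMIS at weeks 2 and 4 does not share it.

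The window counts come straight from the documents. The size of the dilution does not: it rests on how patients weight recalled days, how fast the effect starts, the share of minors and whether the forms are pooled, none of which the plan settles for this outcome.

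**What to change.** - In Section 2.0 a), define the day-2 and day-6 PROMIS outcomes, including the between-dose comparison, for adults completing Appendix F only.
- Use the pediatric form for change from baseline at weeks 2 and 4 only, and align Section 2.0 b) and the Study Calendar with this.
- In Section 7.0 a), state that PROMIS is analysed or reported separately by form at all visits. The plan specifies only t-tests and chi-square tests, so this means separate summaries and tests, not a term added to a model.

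The split depends on age at baseline, so the randomised comparison is kept within each group. The cost is slightly fewer patients in the day-2 and day-6 PROMIS analyses; minors would have two fewer questionnaires. If the early pediatric forms are collected anyway, their scores should be labeled as covering time both before and after injection.
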